3.3.4.1 Discontinuation of trial treatment

An individual patient will permanently discontinue trial treatment if:

- The patient experiences signs of hepatic injury, defined in section [5.2.5.1.4](#)
- In the opinion of the investigator, the patient experiences unacceptable adverse events despite dose adjustments and supportive care.
- The patient has repeatedly shown to be non-compliant with important trial procedures and, in the opinion of both, the investigator and sponsor representative, is not willing or able to adhere to the trial requirements in the future.
- The patient needs to take prohibited concomitant medication as defined in section [4.2.2](#) "Restrictions".
- The patient can no longer receive nintedanib for medical reasons
- Pregnancy: if a patient becomes pregnant during the trial, nintedanib needs to be stopped and the patient should be followed up until birth or otherwise termination of the pregnancy. The data of the patient will be collected and reported in the clinical trial report (CTR) until patient's last visit and any events thereafter will be reported in the BI drug safety database. Refer to section [5.2.5.2.4](#) for detailed information on event reporting in case of pregnancy.

In the following cases discontinuation of nintedanib is highly recommended. Only in special circumstances, the investigator, upon thorough assessment of all available clinical data and taking into consideration the potential risks associated with administration of nintedanib, may decide not to withdraw the trial medication, even though one or more of the below mentioned criteria are fulfilled. In such a case, continuation of treatment with trial medication should be discussed with the patient, and the decision and reasoning documented in the source data.

- Major surgery, including any abdominal or intestinal surgery.
- Anti-coagulation. Patients who require full-dose therapeutic anticoagulation (e.g. vitamin K antagonists, heparin, hirudin, direct thrombin inhibitors, factor Xa inhibitors etc.), or high-dose antiplatelet therapy. (Prophylactic low dose heparin or heparin flush as needed for maintenance of an indwelling intravenous device (e.g. enoxaparin 4000 I.U. s.c. per day), as well as prophylactic use of antiplatelet therapy (e.g. acetyl salicylic acid up to

Proprietary confidential information © 2020 Boehringer Ingelheim International GmbH or one or more of its affiliated companies

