325 mg/day, or clopidogrel at 75 mg/day, or equivalent doses of other antiplatelet therapy is allowed.).

- Major thrombo-embolic events e.g. stroke, deep vein thrombosis, pulmonary embolism, myocardial infarction.

In case of a temporary interruption, trial treatment should be restarted if medically justified, please see section [4.2.1](#).

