4.2 OTHER TREATMENTS, EMERGENCY PROCEDURES, RESTRICTIONS

4.2.1 Other treatments and emergency procedures

Rescue medications to reverse the action of nintedanib are not available.

There are no special emergency procedures to be followed.

Dose reduction (from 150 mg bid to 100 mg bid) or treatment interruption should be considered to manage adverse events. No further dose reduction is possible for patients on the 100 mg bid dose. In case of persistent adverse events observed at this dose, or severe effects at 150 mg bid, permanent treatment discontinuation should be considered.

Dose reduction from 150 mg bid to 100 mg bid was possible at Visit 1 if required to manage adverse events identified at the end of the INBUILD® trial.

Treatment interruption and reduction and re-escalation are repeatedly possible.

Table 4.2.1: 1 Allowed treatment reduction / interruption periods

	AEs considered drug related	AEs or other events not considered drug related
Maximum interruption	4 weeks	12 weeks
Recommended restart	with reduced dose (100 mg bid)	with the same dose (100 mg bid or 150 mg bid)
Re-escalation	Any time to 150 mg bid	----

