4.2.1.2 Management of liver enzyme elevation

Evaluate the concomitant use of other drugs known to cause liver enzyme elevations. For a detailed guidance on how to manage liver enzyme elevations, please refer to Table 4.2.1.2: 1.

Table 4.2.1.2: 1 Management of liver enzyme elevations

AST or ALT increase to			Signs of hepatic injury* (section 5.2.5.1.4)	
>1.5x to <3x ULN	$\geq 3x$ to <5x ULN and no signs of hepatic injury (section 5.2.5.1.4)	$\geq 5x$ to <8x ULN and no signs of hepatic injury (section 5.2.5.1.4)		
Continue as planned ¹	Reduce dose or interrupt trial medication ²	Interrupt trial medication	Permanently discontinue / interrupt trial medication	
	Close observation ³ After 2 weeks or any time later	Close observation ³ After 2 weeks or any time later		CLINICAL EVALUATION OF HEPATIC-INJURY⁴ (section 5.2.5.1.4)
<3x ULN	$\geq 3x$ ULN	< 3x ULN	$\geq 3x$ ULN	
Reduced: return to initial dose. Interrupted: restart at reduced dose. Monitor every 2 weeks for at least 8 weeks	Permanently discontinue trial medication Close observation ³	Restart at reduced dose Monitor weekly for 4 weeks, then every 2 weeks for at least 8 weeks	Permanently discontinue trial medication. Close observation ³	

Footnotes:

*Signs of hepatic injury are defined as

- ALT and/or AST ≥ 8 fold ULN
- ALT and/or AST ≥ 3 fold ULN and total bilirubin ≥ 2 fold ULN
- ALT and/or AST ≥ 3 fold ULN and unexplained INR $> 1,5$
- ALT and/or AST ≥ 3 fold ULN and unexplained eosinophilia ($> 5\%$)
- ALT and/or AST ≥ 3 fold ULN and appearance of fatigue, nausea, vomiting, right upper abdominal quadrant pain or tenderness, fever and/or rash

¹ According to visit schedule. Consider additional control visits as adequate.

² To be decided by Investigator, based on individual risk assessment.

³ Close observation: Re-test ALT and AST, alkaline phosphatase, total bilirubin, and eosinophils within 48 to 72 hours, then after approximately 7 days and after approximately 2 weeks by using intermediate visit lab kit.

⁴ If clear evidence for alternative cause for hepatic injury was identified and resolved (i.e. relation to trial medication excluded, hepatic injury confirmed to have alternative explanation [other than use of IMP]): return to trial medication would be possible, after consultation with the sponsor. Prior to restart, liver laboratory values must be normal. Monitor weekly for first 4 weeks of re-introduction and every 2 weeks for the following 8 weeks.

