5.2.5.1.4 Adverse events of special interest

The term adverse events of special interest (AESI) relates to any specific AE that has been identified at the project level as being of particular concern for prospective safety monitoring and safety assessment within this trial, e.g. the potential for AEs based on knowledge from other compounds in the same class. AESIs need to be reported to the sponsor’s Pharmacovigilance Department within the same timeframe that applies to SAEs, please see section [5.2.5.2.2](#).

Adverse events relating to gastrointestinal perforation and hepatic injury will be considered AESIs.

Hepatic injury

In this trial protocol, signs of hepatic injury are defined as:

- ALT and/or AST \geq 8 fold ULN
- ALT and/or AST \geq 3 fold ULN and total bilirubin \geq 2 fold ULN*
- ALT and/or AST \geq 3 fold ULN and unexplained INR $>$ 1,5*
- ALT and/or AST \geq 3 fold ULN and unexplained eosinophilia ($>5\%$)*
- ALT and/or AST \geq 3 fold ULN and appearance of fatigue, nausea, vomiting, right upper abdominal quadrant pain or tenderness, fever and/or rash

* in the same blood draw sample.

These lab findings constitute a hepatic injury alert and the patients showing these lab abnormalities need to immediately stop the trial medication and need to be followed up according to the “drug-induced liver injury (DILI) checklist” provided in the ISF.

In case of clinical symptoms of hepatic injury (icterus, unexplained encephalopathy, unexplained coagulopathy, right upper quadrant abdominal pain, etc.) without lab results (ALT, AST, total bilirubin) available, the investigator should make sure these parameters are

analysed, if necessary in an unscheduled blood test. Should the results meet the criteria of hepatic injury alert, the procedures described in the DILI checklist should be followed.

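### Protocol 3.3.4.1 makes discontinuation for signs of hepatic injury permanent without exception, but Table 4.2.1.2: 1, footnote 4 allows a conditional restart

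*Protocol*

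**What the plan says.** Protocol 3.3.4.1 has two lists. The first opens "An individual patient will permanently discontinue trial treatment if", and its first entry is "The patient experiences signs of hepatic injury, defined in section" 5.2.5.1.4. The second covers major surgery, anticoagulation and major thrombo-embolic events. For that list alone the investigator, in special circumstances, "may decide not to withdraw the trial medication, even though one or more of the below mentioned criteria are fulfilled". The section closes with a general sentence: "In case of a temporary interruption, trial treatment should be restarted if medically justified, please see section" 4.2.1.

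Protocol 4.2.1.2 deals with the same signs in the last column of Table 4.2.1.2: 1, where the action is "Permanently discontinue / interrupt trial medication". Footnote 4 is attached to the clinical evaluation step in that column. Where there is clear evidence that another cause explains the injury and has resolved, so that a relation to trial drug is excluded, "return to trial medication would be possible, after consultation with the sponsor. Prior to restart, liver laboratory values must be normal". Closer monitoring follows the restart.

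Protocol 5.2.5.1.4 says that patients with these laboratory findings "need to immediately stop the trial medication and need to be followed up according to the" liver-injury checklist. It does not say whether the stop is permanent.

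SAP 6.2, Table 6.2: 1, row C2a describes as an important deviation the failure to stop drug permanently after signs of hepatic injury. It cites protocol 5.2.5.1.4 and 4.2.1.2. Its requirements column limits the deviation to cases not handled as the protocol requires. The row is judged manually and excludes nobody from analysis.

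**The concern.** These are operative stopping rules for an identified safety risk, and they give different instructions for the same patient. If the liver injury proves to have another cause, one section has already ended treatment for good and the other allows a return to drug. Whether that patient is withdrawn or retained then depends on which section the site reads.

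Withdrawal has lasting consequences. Previous enrolment is an exclusion criterion (protocol 3.3.3), so the patient cannot re-enter. After the individual end of trial, new adverse events are no longer actively monitored (5.2.5.2.1). In a trial of long-term tolerability, that gives up follow-up on a patient whom the protocol elsewhere regards as fit to continue.

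**Working it through.** The plan states no figure on this point, so the check is a comparison of rules for one patient: signs of hepatic injury as defined in 5.2.5.1.4, a clear alternative cause found and resolved, the sponsor consulted, and liver values back to normal.

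1. **Under 3.3.4.1.** The signs are on the mandatory list, and discretion is confined to the other list. Discontinuation is permanent. By 6.2.2 the end-of-treatment visit follows as soon as possible after last intake. By 6.2.3 the follow-up visit, 28 days after last intake (+7 in the Flowchart), completes the trial for a patient who stopped because of an adverse event.
2. **Under Table 4.2.1.2: 1.** The stop may be an interruption. All the conditions of footnote 4 are met, so the patient may resume and stays in the trial.
3. **Can both be followed?** No. A patient who has permanently discontinued is not eligible to restart.
4. **Does other text settle it?** The closing sentence of 3.3.4.1 is generic and does not mention hepatic injury. The immediate stop in 5.2.5.1.4 fits either rule. Section 1.4 speaks of withholding drug until recovery from hepatic toxicity in general, but also says that for severe liver enzyme elevations, as specified in 3.3.4, treatment must be discontinued. Section 5.2.3 sends the reader to 4.2.1.2 for monitoring and to 3.3.4 for withdrawal criteria. No rule of precedence is given.
5. **Effect on the analyses.** A withdrawn patient appears under adverse events leading to permanent treatment discontinuation (SAP 7.8.1) and as an event in time to premature discontinuation (SAP 5.4.3.1.1). A restarted patient does not, unless stopped later. With about 480 patients planned, one patient is 1/480 = 0.0021, or 0.21 percentage points. The primary endpoint counts patients with any adverse event. The triggering event already counts on either route, so that proportion does not move.
6. **How many patients.** The documents give no rate for the defined signs. The 22.6% quoted in protocol 1.2 for the parent trial's nintedanib group is for a broad enzyme-elevation safety topic and cannot stand in for it. Footnote 4 then narrows the group to patients with a proven non-drug cause.

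**The case against.** The best defence is that the intended rule can be identified. Footnote 4 is specific, and the log for Global Amendment 1 shows that the restart option was added on purpose. The bullet in 3.3.4.1 is general. No restart can happen on a site's own reading, because the sponsor must be consulted, and a site that stops at 3.3.4.1 errs towards caution. All of this is fair and keeps the point small. It does not remove the conflict, because 1.4 and 5.2.3 send readers to 3.3.4 for discontinuation, and a site that acts there has no reason to call the sponsor about a restart.

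Two stronger readings are tempting.

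- A reader might infer that SAP row C2a is separately wrong because it writes out no exception. But it cites protocol 4.2.1.2, where footnote 4 sits, defers to the protocol's requirements and is reviewed manually. A compliant restart can be judged not to be a deviation. What remains is ambiguity inherited from the protocol.
- A reader might set the 12-week maximum interruption in Table 4.2.1: 1 against the follow-up visit and infer a fixed period in which restart is open under one rule after the trial has ended under the other. That maximum belongs to the column for "AEs or other events not considered drug related". While the cause is still being evaluated, drug relation has not been excluded. For drug-related events the maximum is 4 weeks, which ends no later than the follow-up visit. Footnote 4 states no time limit and does not refer to that table, so the documents fix no such period.

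It can also be said that the discontinuation summaries would still be correct, since they report what happened to each patient. That stands: the difference lies in patient management, and the estimators are sound.

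**Conclusion.** The inconsistency is real. Protocol 3.3.4.1 is unconditional for signs of hepatic injury, and Table 4.2.1.2: 1 with footnote 4 is not. The consequence is that a patient with proven non-drug liver injury may be withdrawn at one site and retained at another.

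The effect is limited. Few patients are likely to be affected, which is a judgement because no rate is given. Each would move the discontinuation proportion by about 0.21 percentage points, assuming the planned 480 are treated. Drug stops at once on both routes, and the primary endpoint is unchanged. The point should be corrected because it governs a safety decision and is cheap to settle. It does not threaten the trial's conclusions.

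**What to change.** In the hepatic-injury bullet of protocol 3.3.4.1, add: *except where restart is permitted under Table 4.2.1.2: 1, footnote 4 (trial medication must still be stopped immediately)*. Do not add a time limit borrowed from Table 4.2.1: 1. That would be a new clinical rule, applied before drug relation has been excluded.

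As an optional conforming edit, add to SAP row C2a: *except restarts meeting CTP Table 4.2.1.2: 1, footnote 4*.

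The cost is one clause in the protocol and, if wanted, one in the SAP. C2 is already a manual review, so no new data collection or programming is needed.

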3.3.4.2 Withdrawal of consent to trial participation

Patients may withdraw their consent to trial participation at any time without the need to justify the decision.

If a patient wants to withdraw consent, the investigator should be involved in the discussion with the patient and explain the options for continued follow up outside of the trial after trial discontinuation, please see section [3.3.4.1](#) above.

Given the patient's agreement, the patient will undergo the procedures for trial discontinuation and follow up (if applicable) as outlined in the [Flowchart](#) and section [6.2.3](#).

3.3.4.3 Discontinuation of the trial by the sponsor

Boehringer Ingelheim reserves the right to discontinue the trial overall or at a particular trial site at any time for the following reasons:

1. Emergence of any efficacy/safety information invalidating the earlier positive benefit-risk-assessment that could significantly affect the continuation of the trial.
2. Patients have alternative access to nintedanib, for example via an alternative clinical trial, marketed product, an expanded access program, named patient use program, compassionate use protocol or other means based on local regulation.
3. Violation of GCP, the trial protocol, or the contract impairing the appropriate conduct of the trial.

The investigator / the trial site will be reimbursed for reasonable expenses incurred in case of trial termination (except in case of the third reason).

4. TREATMENTS

4.1 INVESTIGATIONAL TREATMENTS

4.1.1 Identity of the Investigational Medicinal Products

All patients will be treated with nintedanib in this trial; there is no active comparator or placebo.

Substance:	Nintedanib
Pharmaceutical formulation:	Soft gelatine capsule
Source:	BI Pharma GmbH & Co. KG
Unit strength:	150mg, 100mg
Posology:	Bid
Route of administration:	Oral (swallowed)

4.1.2 Selection of doses in the trial and dose modifications

Based on the efficacy, safety and dose-finding from trials investigating nintedanib in IPF, a dose of 150 mg bid is selected for the PF-ILD program. With 150 mg bid, acceptable tolerability in PF-ILD patients is expected based on the risk profile seen in IPF patients. However to manage adverse events, the dose may be reduced to 100 mg bid temporarily or permanently (see section [4.2.1](#) and section [6.2.2](#)).

The objective of INBUILD® was to assess the efficacy and safety of a dose of 150 mg bid compared to placebo. Patients were randomised either to blinded nintedanib or to blinded placebo 150 mg bid.

Patients taking 150 mg bid blinded study medication (active drug or placebo) at the end of INBUILD® will start treatment with nintedanib 150 mg bid in the current extension trial. Patients taking 100 mg bid blinded study medication (active drug or placebo) at the end of INBUILD® will start treatment with nintedanib in the current extension trial either at 100 mg bid or at an increased dose of 150mg bid at the discretion of the investigator.

For patients who receive nintedanib 100 mg bid in the extension study, at the time of unblinding (final database lock) of the INBUILD® trial, it is allowed to increase the dose to 150 mg bid at the discretion of the investigator, based on the unblinding information. In this situation, dose increase will need to be assigned through IRT, and an additional visit might be required (refer to section [6.2.2](#)).

Nintedanib can be interrupted or reduced without prior interruption, i.e., immediately stepping down from 150 mg bid to 100 mg bid at the discretion of the investigator to manage adverse events. Dose adjustments might require a special trial visit according to the procedures in section [6.2.2](#).

4.1.3 Method of assigning patients to treatment groups

All patients will receive treatment with nintedanib. Interactive Response Technology (IRT) will be used to assign medication numbers to eligible patients. Distribution of nintedanib to sites will be triggered by IRT. Details on the IRT system are provided in the ISF.

4.1.4 Drug assignment and administration of doses for each patient

The treatment for an individual patient will be assigned by means of an IRT contact during Visits 1, 3, 5, 6, 7, 8 to X. Each patient will receive active drug at a dosage of 150mg bid or 100mg bid.

Trial medication will consist of 1 capsule twice daily throughout the trial. Wallets covering 30 days + 5 days reserve treatment will be dispensed to the patient:

- 1 wallet at Day 1 (Visit 1) (30 days plus 5 days reserve)
- 2 wallets at Visit 3 (60 days plus 10 days reserve)
- 3 wallets at Visit 5, Visit 6, Visit 7, Visit 8 and Visit X (90 days plus 15 days reserve)

Nintedanib will be administered orally on a twice daily basis (bid). The patients should swallow the trial medication unchewed together with a glass of water (~250mL), and should observe a dose interval of 12 hours. Nintedanib needs to be taken at the same times every day (between 06:00 and 11:00 in the morning, and between 18:00 and 23:00 in the evening). Because nintedanib may cause stomach discomfort, it is recommended to take the trial medication with food.

A forgotten dose should be skipped if the time window to the next dose is less than 8 hours. The next dose should be taken as scheduled.

Nintedanib should only be dispensed to participating patients according to the protocol by authorised personnel as documented in the form “Trial Staff List”.

4.1.5 Blinding and procedures for unblinding

4.1.5.1 Blinding

In this open-label trial, treatment allocation will not be concealed throughout the trial. The CRF will contain information on actual treatment.

The previous treatment received in INBUILD® (active drug or placebo) will remain unknown to the investigator and patient until after the final database lock of INBUILD®. No individual unblinding regarding treatment received in INBUILD® should occur prior to this time.

4.1.5.2 Unblinding and breaking the code

Not applicable.

4.1.6 Packaging, labelling, and re-supply

The investigational medicinal products will be provided by BI or a designated clinical research organisation (CRO). They will be packaged and labelled in accordance with the principles of Good Manufacturing Practice (GMP). Initial supply and re-supply to the sites will be managed via an IRT system, which will also monitor expiry dates of supplies available at the sites, and assign treatment kits to each patient.

For details of packaging and the description of the label, refer to the ISF.

Primary trial material will be capsules containing 150 mg of nintedanib (or 100 mg of nintedanib if dose is reduced). All trial medication will be packaged in blister cards. Each blister card will contain 10 capsules. Seven blisters cards will be packaged into one child-resistant tamper-evident wallet (i.e. 70 capsules/wallet). Each wallet will be labelled with a multi-language booklet according to the requirements of the participating countries.

One wallet provides for one month of treatment.

Re-supplies of trial medication are planned due to the short expiry date and the long duration of the trial. The medication for re-supply will be packaged in an identical manner as the medication for initial supply.

4.1.7 Storage conditions

Drug supplies will be kept in their original packaging and in a secure limited access storage area according to the recommended storage conditions on the medication label. A temperature log must be maintained for documentation.

If the storage conditions are found to be outside the specified range, the local clinical monitor (as provided in the list of contacts) must be contacted immediately.

